11. MANAGEMENT AND REPORTING OF ADVERSE EVENTS/ADVERSE REACTIONS

11.1 Adverse Events

Each AE from the point of enrolment until study completion will be described on the AE e-CRF using the medical diagnosis (preferred), or, if no diagnosis could be established at the time of reporting the AE, a symptom or sign, in standard medical terminology in order to avoid the use of vague, ambiguous, or colloquial expressions (see definitions in Section 11.1.1). Each AE will be evaluated by the investigator for:

- Seriousness as defined in Section 11.1.1.1
- Severity as defined in Section 11.1.2.1
- Causal relationship to medicinal product exposure as defined in Section 11.1.2.2

For each AE, the outcome (ie, recovering/resolving, recovered/resolved, recovered/resolved with sequelae, not recovered/not resolved, fatal, unknown) and action taken (ie, dose increased, dose not changed, dose reduced, drug interrupted, drug withdrawn, not applicable, or unknown) will also be recorded on the AE e-CRF. Recovering/resolving AEs will be followed until resolution, medically stabilized, or 30 days after the study completion/termination visit, whichever comes first.

11.1.1 Definitions

An AE is defined as any untoward medical occurrence in a subject administered a medicinal product that does not necessarily have a causal relationship with the treatment. An AE can therefore be any unfavorable and unintended sign (eg, an abnormal laboratory finding), symptom (eg, rash, pain, discomfort, fever, dizziness, etc.), disease (eg, peritonitis, bacteremia, etc.), or outcome of death temporally associated with the use of a medicinal product, whether or not considered causally related to the medicinal product

11.1.1.1 Serious Adverse Event

A **serious** adverse event (SAE) is defined as an untoward medical occurrence that at any dose meets one or more of the following criteria:

- Outcome is fatal/results in death (including fetal death)
- Is life-threatening – defined as an event in which the subject was, in the judgment of the investigator, at risk of death at the time of the event; it does not refer to an event that hypothetically might have caused death had it been more severe.
- Requires inpatient hospitalization or results in prolongation of an existing hospitalization – inpatient hospitalization refers to any inpatient admission, regardless of length of stay.

- Results in persistent or significant disability/incapacity (ie, a substantial disruption of a person's ability to conduct normal life functions)
- Is a congenital anomaly/birth defect
- Is a medically important event – a medical event that may not be immediately life-threatening or result in death or require hospitalization but may jeopardize the subject or may require medical or surgical intervention to prevent one of the other outcomes listed in the definitions above. Examples of such events are:
 - Intensive treatment in an emergency room or at home for allergic bronchospasm, blood dyscrasias, or convulsions that do not result in hospitalization, or development of drug dependence or drug abuse
 - Reviewed and confirmed seroconversion for human immunodeficiency virus (HIV), hepatitis A virus (HAV), hepatitis B virus (HBV), hepatitis C virus (HCV), hepatitis E virus (HEV), or parvovirus B19 (B19V)

For this study in particular, medically important events include:

- Thromboembolism/DIC/Fibrinolysis
- Reviewed and confirmed inhibitor development
- Nephrotic syndrome.

Uncomplicated pregnancies, following maternal or paternal exposure to product are not considered an (S)AE; however, any pregnancy complication or pregnancy termination by therapeutic, elective, or spontaneous abortion shall be considered an SAE.

11.1.1.2 Non-Serious Adverse Event

A **non-serious** AE is an AE that does not meet the criteria of an SAE.

11.1.1.3 Unexpected Adverse Events

An unexpected AE is an AE whose nature, severity, specificity, or outcome is not consistent with the term, representation, or description used in the Reference Safety Information (eg, package insert). “Unexpected” also refers to the AEs that are mentioned in the package insert as occurring with a class of drugs or as anticipated from the pharmacological properties of the drug, but are not specifically mentioned as occurring with the particular drug under investigation.

11.1.1.4 Preexisting Diseases

Preexisting diseases that are present before entry into the study are described in the medical history, and those that manifest with the same severity, frequency, or duration during the study, will not be recorded as AEs/SAEs. However, when there is an increase in the severity, duration, or frequency of a preexisting disease, the event must be described on the AE CRF. Bleeding events will not be considered as AEs if they do not qualify as an SAE.

11.1.2 Assessment of Adverse Events

For the purposes of this study, the following events experienced after enrollment will not be considered AEs, and thus, not included in the analysis of AEs:

- Bleeding events:
will not be considered as AEs if they do not qualify as an SAE
- Elective surgeries:
Elective and planned surgeries when these surgeries relate to a preexisting disease (see also 11.1.1.4) that has not worsened during study participation will not be considered as (S)AEs

Each AE from enrollment until study completion or withdrawal will be described on the AE CRF using the medical diagnosis (preferred), or, if no diagnosis could be established at the time of reporting the AE, a symptom or sign, in standard medical terminology in order to avoid the use of vague, ambiguous, or colloquial expressions (see definitions in Section 11.1). Each AE will be evaluated by the investigator for:

- Seriousness as defined in Section 11.1.1.1
- Severity as defined in Section 11.1.2.1
- Causal relationship to medicinal product exposure as defined in Section 11.1.2.2.

For each AE, the outcome (ie, recovering/resolving, recovered/resolved, recovered/resolved with sequelae, not recovered/not resolved, fatal, unknown) and if applicable action taken (ie, dose increased, dose not changed, dose reduced, drug interrupted, drug withdrawn, not applicable, or unknown) will also be recorded on the AE CRF. Recovering/resolving AEs will be followed until study completion or withdrawal. If the severity rating for an ongoing AE changes before the event resolves, the original AE report will be revised (ie, the event will not be reported as separate AE). During the course of any AE, the highest severity rating will be reported.

Deviations from the dosage specified in the package insert (including overdosing, underdosing, abuse, and withdrawal) treatment errors (including incorrect route of administration, use of an incorrect product, and deviations from the dosing schedule defined in the package insert), failures of expected pharmacological actions, and unexpected therapeutic or clinical benefits will be followed with regard to occurrence of AEs, lack of efficacy, and/or other observations because these events may be reportable to regulatory authorities. Definition of under- and overdosing is done as per the judgement of the treating physician.

Any pregnancy that occurs after administration of medicinal product will be reported on a Pregnancy Form and followed-up at 1 year post-delivery, if feasible.

11.1.2.1 Severity

The investigator will assess the severity of each AE using his/her clinical expertise and judgment based on the most appropriate description below:

- Mild
 - The AE is a transient discomfort and does not interfere in a significant manner with the subject's normal functioning level.
 - The AE resolves spontaneously or may require minimal therapeutic intervention.
- Moderate
 - The AE produces limited impairment of function and may require therapeutic intervention.
 - The AE produces no sequela/sequelae.
- Severe
 - The AE results in a marked impairment of function and may lead to temporary inability to resume usual life pattern.
 - The AE produces sequela/sequelae, which require (prolonged) therapeutic intervention.

11.1.2.2 Causality

Causality is a determination of whether there is a reasonable possibility that the medicinal product/is etiologically related to/associated with the AE. Causality assessment includes, eg, assessment of temporal relationships, dechallenge/rechallenge information, association (or lack of association) with underlying disease, presence (or absence) of a more likely cause, and physiological plausibility. For each AE, the investigator will assess the causal relationship between the medicinal product and the AE using his/her clinical expertise and judgment according to the following most appropriate algorithm for the circumstances of the AE:

- Not related (both circumstances must be met)
 - Is due to underlying or concurrent illness, complications, concurrent treatments, or effects of concurrent drugs
 - Is not associated with the medicinal product (ie, does not follow a reasonable temporal relationship to the administration of product or has a much more likely alternative etiology).
- Unlikely related (either 1 or both circumstances are met)
 - Has little or no temporal relationship to the medicinal product
 - A more likely alternative etiology exists
- Possibly related (both circumstances must be met)
 - Follows a reasonable temporal relationship to the administration of medicinal product
 - An alternative etiology is equally or less likely compared to the potential relationship to the medicinal product
- Probably related (both circumstances must be met)
 - Follows a strong temporal relationship to the administration of medicinal product which may include but is not limited to the following:
 - Reappearance of a similar reaction upon re-administration (positive rechallenge)
 - Positive results in a drug sensitivity test (skin test, etc.)
 - Toxic level of the product as evidenced by measurement of the product concentrations in the blood or other bodily fluid
 - Another etiology is unlikely or significantly less likely.

For events assessed as not related or unlikely related and occurring within 30 days, the investigator shall provide the alternative etiology.

11.2 Non-Medical Complaints

A non-medical complaint (NMC) is any alleged product deficiency that relates to identity, quality, durability, reliability, safety, effectiveness, or performance of the product but **does not result in an AE**. NMCs include but are not limited to the following:

- A failure of a product to exhibit its expected pharmacological activity and/or design function
- Missing components
- Damage to the product or unit carton
- A mislabeled product (potential counterfeiting/tampering)
- A bacteriological, chemical, or physical change or deterioration of the product that causes it to malfunction or to present a hazard or fail to meet label claims

Any NMCs of the product will be documented on an NMC form and reported to the MAH within 1 business day. If requested, defective product(s) will be returned to the MAH for inspection and analysis according to procedures.

12. PLANS FOR DISSEMINATING AND COMMUNICATING STUDY RESULTS

The investigator will comply with the publication policy as described in the Non-interventional Trial Agreement.

The investigator, or coordinating investigator(s) for multicenter studies, will sign the study report

14. ANNEXES

14.1 List of Stand-Alone Documents

No.	Date	Title
1	TBD	Study Roster
2	TBD	Clinical Monitoring Plan
3	TBD	Data Management Plan
4	TBD	Statistical Analysis Plan

14.2 ENCePP Checklist for Study Protocols

Refer to the completed ENCePP Checklist.

14.3 Additional Information

List of Definitions

Important terms	Definitions
Chronic pain:	Continuous and/or intermittent pain, related to the pathophysiology of hemophilia, requiring intervention (pharmacological or non-pharmacological treatment), and in which the cause of pain cannot be readily removed, occurring more than once a week and lasting 3 months or more”
Episodic prophylaxis	Episodic prophylaxis lasting no more than 3 months.
High responding inhibitors:	“inhibitors with peak activity >5 Bethesda Units (BU/mL) associated with anamnesis following replacement of the missing clotting factor.” and this level >5 BU/mL “is maintained at any time”.
On-demand treatment	Treatment of acute bleeds with any factor concentrates with the goal to resolve bleeds
Prophylaxis	Regular administration of factor concentrates with the goal to prevent bleeds. For analysis purposes, in this protocol, Hemophilia B prophylaxis is defined as follows: at least one administration per week. Long term prophylaxis lasting for one year or more. Short term prophylaxis lasting for more than 3 months.
Target Joint	A target joint is defined as a joint in which at least 3 or more spontaneous bleeds into a single joint within a consecutive 6 month period. Where there have been ≤ 2 bleeds into the joint within a consecutive 12 month period the joint is no longer considered a target joint (Blanchette et al 2014) ¹⁹

APPENDIX 1

Assessment of effectiveness

Total number (%) of treated bleeds and their corresponding hemostatic effectiveness ratings using an “excellent-to-poor” 4-point Likert scale by the subjects/care-giver (subjects <12 years: care-giver, subjects ≥ 12 years: self assessment) for treatments given at home, or by the investigator for treatments given in the hospital/clinic.

Excellent	Full relief of pain and cessation of objective signs of bleeding (e.g., swelling, tenderness, and decreased range of motion in the case of musculoskeletal hemorrhage) within approximately 6 hours to 12 hours and after 1 or 2 infusions. No additional infusion is required for the control of bleeding. Any additional infusion for treatment of bleeding will preclude this rating. Administration of further infusions to maintain hemostasis would not affect this scoring.
Good	Definite pain relief and/or improvement in signs of bleeding within approximately 6 hours to 24 hours requiring more than 2 infusions for complete resolution. Administration of further infusions to maintain hemostasis would not affect this scoring.
Fair	Probable and/or slight relief of pain and slight improvement in signs of bleeding within approximately 6 hours to 24 hours. Requires multiple infusions for complete resolution.
Poor	No improvement of signs or symptoms or conditions worsen.

For prevention of bleeding episodes:

Annualized (ABR) and/or monthly bleeding rate (MBR), all bleeds, will be calculated as appropriate, based on the following formula: $ABR = (\text{number of bleeds/observational period days}) \times 365.25$; $MBR = (\text{number of bleeds/observational period} - \text{days}) \times 30.44$

- ✓ ABR and/or MBR will be calculated as appropriate, in all joint bleeding events
- ✓ Assessment of hemostatic effectiveness
 - The effectiveness will be assessed by a “excellent-to-poor” 4-point Likert scale by the subjects/care-giver (subjects <12 years: care-giver, subjects ≥ 12 years: self assessment) at the end of each prophylaxis period (if possible rated within 24 hours from the end of the prophylactic treatment) or on an annual basis, whichever occurs first.

Table 4 Overall Effectiveness Assessment for Prophylaxis Therapy	
Excellent	Definitely low bleeding rate with improvement in daily activities and quality of life. Very satisfied with the treatment and worth being continued-
Good	Relatively low bleeding rate with some improvement in daily activities and quality of life. Satisfied with the treatment and worth being continued-
Fair	Relative increase in breakthrough bleeding episodes with only partial benefit in terms of activity level and quality of life. Partially satisfied with the treatment. Not sure if it is worth continuing treatment
Poor	Frequent breakthrough bleeding episodes interfering with activity level and quality of life. Not satisfied with the treatment.

APPENDIX 2

The Hemophilia Joint Health Score (HJHS)¹⁷ was developed by the International Prophylaxis Study Group (IPSG) as a new scoring system for musculoskeletal evaluation optimized for use in children with no or minimal joint disease. The HJHS is better suited for children aged 4–18 years and all patients on primary prophylaxis than the Gilbert score, which was found to be too insensitive to identify earliest signs of joint disease. The HJHS includes the following parameters: swelling, duration of swelling, muscle atrophy, joint pain, crepitus on motion, flexion loss, extension loss, strength and global gait. The HJHS measures joint health, in the domain of body structure and function (i.e. impairment), of the joints most commonly affected by bleeding in hemophilia: the knees, ankles, and elbows. It can be used when there is a need for orthopedic intervention, or as an outcome measure of physiotherapy interventions. It is appropriate for monitoring joint change over time or assessing effectiveness of treatment regimens in children receiving both prophylactic and on-demand therapy. The HJHS 2.1 provides a total score (higher score is worse; max=124), joint specific scores, and a global gait score. See [Table 5](#). The HJHS total score, calculated from the Sum of Joint Totals and Global Gait Score will be collected during screening, annual, and termination visits or whenever the treating physician deems it appropriate.

Table 5 Hemophilia Joint Health Score (HJHS) for assessing Joint Impairment	
Swelling	0 = no swelling 1 = mild 2 = moderate 3 = severe
Duration (swelling)	0 = no swelling or < 6 months 1 = ≥6 months
Muscle Atrophy	0 = none 1 = mild 2 = severe
Joint Pain	0 = no pain through active range of motion 1 = no pain through active range, only pain on gentle overpressure or palpation 2 = pain through active range
Crepitus on Motion	0 = none 1 = mild 2 = severe
Flexion Loss	0 = < 5° 1 = 5° - 10° 2 = 11° - 20° 3 = > 20°
Extension Loss (from hyperextension)	0 = < 5° 1 = 5° - 10° 2 = 11° - 20° 3 = > 20°
Strength (using the Daniels & Worthingham's scale)	Within available ROM 0 = holds test position against gravity with maximum resistance (gr.5) 1 = holds test position against gravity with moderate resistance (but breaks with maximal resistance) (gr.4) 2 = holds test position with minimal resistance (gr.3+), or holds test position against gravity (gr. 3) 3 = able to partially complete ROM against gravity (gr.3-/2+), or through partial ROM gravity eliminated (gr.2-) 4 = Trace (gr.1) or no muscle contraction (gr.0) NE = non-evaluable
Global Gait (walking, stairs, running, hopping on 1 leg)	0 = all skills are within normal limits 1 = one skill is not within normal limits 2 = two skills are not within normal limits 3 = three skills are not within normal limits 4 = four skills are not within normal limits NE = non-evaluable

Source: Feldman et al, 2008, HJHS Summary Score Sheet at (last accessed August 2014)
http://www1.wfh.org/docs/en/Publications/Assessment_Tools/HJHS_Summary_Score.pdf

- Radiographs using the Pettersson scale (if available)
- The World Federation of Hemophilia endorsed a radiographic scale, commonly referred to as the Pettersson scale ¹⁸ to measure hemophilia joint health status. Eight parameters are weighted and summed to give a score for the joint as shown in [Table 6](#). Pettersson scores of all joints will be collected during screening, intervals, and termination visits or whenever the treating physician deems it appropriate.

Table 6 Pettersson Scale for Radiographic Evaluation of Hemophilic Joints	
X-Ray	
Osteoporosis: Absent: 0 Present: 1
 
Enlarged epiphysis: Absent: 0 Present: 1
 
Irregular subchondral surface: Absent: 0 Surface partially involved: 1 Surface totally involved: 2
 
Narrowing of joint space: Absent: 0 Present with joint space <1 mm: 1 Present with joint space >1 mm: 2
 
Subchondral cyst formation: Absent: 0 1 cyst: 1 >1 cyst: 2
 
Erosion at joint margins: Absent: 0 Present: 1
 
Gross incongruence of articulating bone ends: Absent: 0 Slight: 1 Pronounced: 2
 
Joint deformity (angulation and/or displacement between articulating bones): Absent: 0 Slight: 1 Pronounced: 2

Source: Pettersson H et al 1980 ¹⁸

- Magnetic Resonance Imaging scoring system (if available and used at site)
- Several MRI scoring systems have been developed to measure hemophilia joint health status. One of the most commonly used systems was one that was developed in Lund, Sweden²³. MRI scores of all joints will be collected during screening, intervals, and termination visits or whenever the treating physician deems it appropriate. The scoring system^{24;25;26} used shall be determined by the subject's radiologist.

Table 7 Magnetic Resonance Imaging Scoring System Developed in Lund, Sweden	
A Component	Subchondral Cyst Present in at least 1 bone Present in at least 2 bones >3 cysts in at least 1 bone >3 cysts in at least 2 bones Largest size >4 mm in at least 1 bone Largest size >4 mm in at least 2 bones Irregularity/erosion of subchondral cortex Present in at least 1 bone Present in at least 2 bones Involve more than half of joint surface in at least 1 bone Involve more than half of joint surface in at least 2 bones Chondral destruction Present in at least 1 bone Present in at least 2 bones Full thickness defect in at least 1 bone Full thickness defect in at least 2 bones Full thickness defect involve s >1/3 of joint surface in at least 1 bone Full thickness defect involves >1/3 of joint surface in at least 2 bones
Effusion/hemarthrosis (e)	Full thickness defect involves >1/3 of joint surface in at least 2 bones
Hypertrophic synovial (s)	0 absent
Hemosiderin (h)	1 equivocal 2 small 3 moderate 4 large

Source: Lundin B et al. 2004²³

INVESTIGATOR ACKNOWLEDGEMENT

PARIXS

STUDY TITLE: Post Authorization RIXUBIS Study

PROTOCOL IDENTIFIER: 251401

ORIGINAL 20 MAR 2015

OTHER PROTOCOL ID(s)

NCT Number: TBD

EudraCT Number: TBD

By signing below, the investigator acknowledges that he/she has read and understands this protocol, understands and abides by the requirements for maintenance of source documentation, and provides assurance that this study will be conducted according to all requirements as defined in this protocol, Non-interventional Trial Agreement, good pharmacovigilance practices, and all applicable regulatory requirements. If applicable, he/she will comply with the requirements for obtaining informed consent from all study subjects prior to initiating any protocol-specific procedures and for obtaining written initial and ongoing ethics committee(s) protocol review and approval.

Signature of Principal Investigator

Date

Print Name of Principal Investigator

Signature of MAH Representative

Date

[name]

Vice President, Clinical Development

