9.7 Data Analysis

9.7.1 Datasets and Analysis Cohorts

The effectiveness analysis will be carried out on the primary and secondary endpoints of the study for the following treatment regimens:

- Standard prophylaxis
- On-demand treatment
- Episodic prophylaxis
- ITI

Effectiveness of switch from on-demand to prophylaxis dataset (ESODTP)

Evaluation of effectiveness (ABR, AJBR) after switch from on-demand regimen to prophylaxis in moderate moderately severe and severe hemophilia B patients.

Safety Analysis Set (SAS)

The SAS will consist of data for all subjects who were enrolled, met all inclusion and none of the exclusion criteria, and received at least 1 infusion of FIX (RIXUBIS). If 2 or more AEs are reported together as a unit, the individual Medical Dictionary for Regulatory Activities (MedDRA) preferred terms will be counted as separate events.

Effectiveness Full Analysis Set (EFAS)

The EFAS will consist of data from all subjects who were enrolled, met all inclusion and none of the exclusion criteria. This dataset will be used for the primary effectiveness analysis for the comparison of annualized bleeding rates (ABR, AJBR) between each independent treatment regimen (i.e., prophylaxis, on-demand).

Calculation of Annualized Bleeding Rates (ABR) and monthly Bleeding Rate (MBR)

The ABR will be calculated as follows: $(\text{total number of bleeding episodes} \div \text{observed treatment period in days}) * 365.25$. The monthly bleeding rates (MBR) will be calculated as follows: $(\text{total number of bleeding episodes} \div \text{observed treatment period in days}) * 30.5$. The treatment period for surgeries will be excluded from the bleed rate calculation.

Bleeding occurring prior to the first prophylactic infusion will not be included in the estimation of bleeding rate. The observation period for the on-demand regimen will commence on the day of enrollment (met all inclusion and none of the exclusion criteria); the period for prophylaxis will commence at the first prophylactic infusion once enrolled (met all inclusion and none of the exclusion criteria).

Minimal Observed Treatment Period to Estimate ABR

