For enrolled subjects that have met all inclusion and none of the exclusion criteria, subjects who have at least 1 assessment [defined as having a minimum of 3-month (≥ 90 days) observational period on regimen] but do not complete the full study period of four years, the ABR will be estimated from the interval assessments. For subjects who do not have at least 1 interval assessment, the median rate observed for the assigned regimen will be substituted.

Health Related Quality of Life Analysis Set (HRQoLAS)

The HRQoLAS will consist of all subjects who have been enrolled and met all inclusion and none of the exclusion criteria and who have provided any available assessments at any available study visit.

Pharmacoeconomics Analysis Set (PEAS)

The PEAS will consist of all the subjects that have been enrolled, met all inclusion and none of the exclusion criteria and have provided any available assessments at any available study visit.

Joint Health/Function Analysis Set (JHFAS)

The JHFAS will consist of all subjects who have been enrolled, met all inclusion and none of the exclusion criteria and have provided any available assessments at any available study visit.

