9.7.3.2 Methods of Analysis for Effectiveness Endpoints

The method of analysis will be applied to the effectiveness endpoint. The primary endpoint, ABR of all types of bleeding episodes, will be calculated for each subject and described for prophylaxis.

In addition, separate description of ABR will be provided for each of the following treatment regimens, assuming a minimum observed period of (≥ 90 days) is fulfilled:

- Standard prophylaxis
- On-demand treatment
- Episodic prophylaxis
- ITI

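### Episodic prophylaxis is capped at 3 months, but its bleeding rate is described only from 90 days on regimen, so a single course almost never qualifies; where regular prophylaxis of 3 months or less belongs is left open

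*Protocol*

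**What the plan says.** Section 14.3 (List of Definitions) sets an upper limit: "Episodic prophylaxis lasting no more than 3 months". For prophylaxis it gives a frequency criterion for analysis, "Hemophilia B prophylaxis is defined as follows: at least one administration per week", followed by two duration lines: long term, of one year or more, and "Short term prophylaxis lasting for more than 3 months".

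Section 9.7.3.2 makes the ABR of all bleeds the primary endpoint, which "will be calculated for each subject and described for prophylaxis". It then adds a separate ABR for standard prophylaxis, on-demand treatment, episodic prophylaxis and ITI, "assuming a minimum observed period of (≥ 90 days) is fulfilled".

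Section 9.7.1, on the minimal period for estimating an ABR, requires at least one assessment, "defined as having a minimum of 3-month (≥ 90 days) observational period on regimen". Its fallback is: "For subjects who do not have at least 1 interval assessment, the median rate observed for the assigned regimen will be substituted". The same section says that "the period for prophylaxis will commence at the first prophylactic infusion once enrolled", with no minimum duration in that sentence. Section 9.7.3.4.1 words the threshold for on-demand treatment as strictly more than 90 days.

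**The concern.** About 90 days is the ceiling in the definition of episodic prophylaxis and the floor in the rule for describing its ABR. If both are applied to one course, a regimen result that the protocol lists by name has almost no eligible data. The fallback does not help, because it borrows a median from observed rates in the same regimen, and those are the rates that are missing.

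The same definitions affect the primary endpoint. Regular weekly prophylaxis that ends at or before 3 months is neither short term nor long term as 14.3 describes them, yet it meets the frequency criterion. The protocol does not say whether such a period is episodic or is prophylaxis with too little observation. The boundary of the primary cohort is therefore open, and so is the question of whose bleeds count in it.

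**Working it through.** The protocol states no figure for the size of the episodic stratum, so there is nothing to reproduce. The check has three steps.

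**1. Overlap for a single course.** Inputs: duration of at most 3 months (14.3) and at least 90 days on regimen (9.7.1, 9.7.3.2). The month lengths are the protocol's own 30.5 days (9.7.1) and 30.44 days (Appendix 1), plus 365.25/12, 30 days and calendar months. The qualifying whole days are those from 90 up to 3 × month length.

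| Month length | Upper limit (days) | Days meeting both rules | Share of possible durations |
|---|---|---|---|
| 30.5 | 91.5 | 90, 91 | 2/91 = 2.2% |
| 30.44 | 91.32 | 90, 91 | 2/91 = 2.2% |
| 365.25/12 | 91.31 | 90, 91 | 2/91 = 2.2% |
| 30 | 90 | 90 | 1/90 = 1.1% |
| Calendar | 89 to 92 | none to three (90–92) | 0 to 3/92 = 3.3% |

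The calendar row covers every start date from 30 April 2015 to 30 September 2021, the last start that leaves three months before the planned end of data collection. These shares count possible durations; they do not predict how many subjects would qualify. With the strict wording of 9.7.3.4.1 (more than 90 days), only day 91 remains in the first three rows, and none with 30-day months.

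**2. If courses are added within a subject.** The number of courses needed is 90 divided by course length, rounded up: 2 courses of 60 or 45 days, 3 of 30 days, or 7 of 14 days. Over a planned 4-year follow-up (9.2.2) this is possible, so the stratum is not empty by construction on this reading. The protocol does not say whether courses are added.

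**3. Regular prophylaxis of under 90 days.** Let p be the fraction of prophylaxis starters affected, s their own mean rate, L the mean rate of the rest, and M the observed regimen median.

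- Mean using everyone's own bleeds: (1 − p)L + p·s.
- Relabelled as episodic: L, which differs by −p(s − L).
- Kept, with the median substituted: (1 − p)L + p·M, which differs by −p(s − M).

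In both cases s drops out of the reported mean. The sign depends on whether s is above or below L (or M). The protocol gives none of p, s, L or M for this cohort. One exception: a period of 90 to 92 days that is kept as prophylaxis contributes its own bleeds.

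**The case against.** The cap in 14.3 limits how long an episode of prophylaxis lasts, while the 90-day rule concerns a subject's observed time on regimen. Section 9.7.1 divides total bleeds by observed days, so adding several courses is a natural reading, and such detail may be settled in the statistical analysis plan. This stands in part: it is why the finding is limited to a single course. But the protocol itself fixes both limits and equates 3 months with 90 days, so the conflict is in the protocol's own wording.

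The episodic ABR is also an additional description in a descriptive study whose size has no statistical basis (9.5), and it is conditional on the minimum period, so it may legitimately go unreported. That lowers the weight of the point without removing it.

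A reader might infer that short prophylaxis drops out of the prophylaxis cohort and that this favours the product. The documents support neither. No section says that regimen is classified by realised duration. The duration lines in 14.3 can be read as subtypes beneath the frequency criterion; 9.7.1 refers to the assigned regimen, starts the prophylaxis period at the first prophylactic infusion, and substitutes a median for a subject with too little observation instead of removing the subject. The selection would be on duration, with no stopping fraction, reason for stopping or bleeding rate in stoppers given, so any percentage bias would rest on invented inputs.

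**Conclusion.** The definition of episodic prophylaxis and the 90-day rule are nearly mutually exclusive for a single course: the overlap is 0 to 3 days. Unless courses are added within a subject, the planned episodic ABR has almost no directly observed data and the substituted median almost no basis.

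Separately, the protocol leaves open whether regular prophylaxis of 3 months or less is prophylaxis or episodic. On either reading, a subject with under 90 days does not bring their own bleeds into the primary prophylaxis ABR. The resulting bias has no size or direction that can be derived from the documents.

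This should be fixed. It concerns one additional stratum and the boundary of the primary cohort, and no sample-size or power figure depends on it.

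**What to change.** - **Episodic prophylaxis:** exempt it from the 90-day rule and from median substitution. Report total bleeds divided by total person-days on episodic prophylaxis, pooled over courses, with a 95% CI that allows for repeated courses within a subject (for example a robust variance or bootstrap clustered on subject). Keep the existing exclusion of surgery periods.
- **Assignment of periods:** for analysis, assign each period to the regimen recorded in the e-CRF at its start, whatever its eventual length.
- **Prophylaxis:** beside the per-subject ABR, add a pooled rate of bleeds over person-days that includes periods under 90 days with their own observed bleeds. Assignment by starting regimen is not enough alone, because the substitution rule in 9.7.1 would still replace those bleeds with the median.
- **Reconcile** 9.7.1, 9.7.3.2, 9.7.3.4.1 and 14.3, including the at-least versus more-than 90-day wording, and state whether courses are added within a subject wherever a minimum period is kept.

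The cost is wording in the definitions and analysis sections. The regimen, dose and frequency are already recorded (9.2.1), as are regimen start and change dates where available (9.2.6), and 9.7.3 already foresees 95% confidence intervals for selected estimates. No treatment rule changes.
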